**Revision Date: April 4, 2019 – Increased enrollment number from 150 to 168**

## **Lay Summary**

Systemic lupus erythematosus (SLE or lupus) is a chronic disease that predominantly strikes young African American women. Because SLE can potentially affect all organs and system, it has a substantial impact on the physical and psychological functioning of patients. Consequently, people living with lupus must engage in challenging self-management tasks to promote their wellbeing. For instance, patients are burdened with managing an array of medical symptoms and often expensive medications. Patients are also challenged with the emotional sequelae of a debilitating and painful condition, and are forced to make undesirable lifestyle changes. Successful self-management of SLE requires having the skills to engage in effective daily activities, which often comes from having access to up to date health education and self-management support.

Although self-management support is crucial to help patients to take control of their disease, no SLE-specific self-management program is widely available. The Chronic Disease Self-Management Program (CDSMP) or Living Well with a chronic condition Program is a nationwide accessible community-based self-management education program that contributes to improved health in people with a variety of chronic conditions. Because the CDSMP is widely disseminated and available to the adult U.S. population through community centers, it may be a suitable and accessible option for African Americans with SLE, even though it is not specifically tailored to SLE or to African Americans. As the CDSMP has been primarily evaluated in predominantly white middle-class seniors with more common diseases (e.g. osteoarthritis, diabetes), the effectiveness of the CDSMP in helping African American women to self-manage SLE is unknown. This study will examine the effectiveness of the CDSMP to improve outcomes and reduce health care utilization in African American women with lupus.

## **BACKGROUND**

Systemic lupus erythematosus (SLE) is a chronic autoimmune disease characterized by multi-system symptoms and an unpredictable course. SLE disproportionately strikes African American (AA) women of childbearing age. AA women with SLE at any age have significantly greater morbidity and mortality compared to Whites. Notably, AA women with SLE have been underrepresented in intervention research, which may be contributing to the existing health disparities and racial gaps in effective disease management.

Because SLE impacts physical and psychological functioning, patients are burdened with managing an array of medical symptoms and often expensive medications, are challenged with the emotional sequelae of a debilitating and painful condition, and are forced to make undesirable lifestyle changes. Successful self-management of SLE requires having the skills to engage in effective daily activities, which often comes from having access to up to date health education and self-management support.

Self-management support is the provision of interventions to increase patients' skills and confidence in managing their diseases, including assessment of problems, goal-setting, action-planning, and problem-solving strategies. Although self-management support is crucial to help patients to take control of their disease, no SLE-specific self-management program is widely available.

The Chronic Disease Self-Management Program (CDSMP), also known as the Living Well Program, is an evidence-based nationwide accessible community-based self-management education program that contributes to improved health in people with a variety of chronic conditions. Because the CDSMP is widely disseminated and available to the adult U.S. population through community centers, it may be a suitable and accessible option for African Americans with SLE, even though it is not specifically tailored to SLE or to African Americans. As the CDSMP has been primarily evaluated in predominantly white middle-class seniors with more common diseases (e.g. osteoarthritis, diabetes), the effectiveness of the CDSMP in helping African American women to self-manage SLE is unknown. This study will examine the effectiveness of the CDSMP to improve outcomes and reduce health care utilization in African American women with lupus.

## **Design Overview**

A random sample selected from our GOAL cohort will be used to recruit AA women with SLE into the WELL (Women Empowered to Live with Lupus) cohort. WELL participants will attend the CDSMP classes in the community, along with people with other chronic illnesses. Measures will be completed at baseline, 6, 12, and 18 months. AA women from the GOAL cohort non-selected to be assigned to the intervention will comprise the usual care group. They will continue their routine annual assessments as part of the GOAL cohort efforts.

We will also conduct a longitudinal qualitative substudy to learn about African American women's perspectives on (a) the processes through which the CDSMP affects self-management behaviors, health-related quality of life (HQRL), and healthcare service use; and (b) identify remaining challenges to successful SLE self-management after CDSMP participation.

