### Recruitment and Informed Consent

A random sample of SLE patients already recruited into the population-based GOAL study will be offered the opportunity to participate in the WELL Sub-study. Target enrollment will be 150 African American women who are resident of one of the metropolitan Atlanta counties where community-based CDSMP classes are provided. [Enrollment number increased to 168 to accommodate participants on a waiting list due to workshop cancellations and participants' rescheduling needs (e.g., illness, hospitalizations, and family emergencies)]. Each woman will have the same probability of being chosen at any stage of the sampling process. Thus, we will ensure

Table 1. Summary of Study Measures		
Category	Measure	Tool
Self-management Behaviors	Communication with Physicians	3-item scale
	Medication Adherence	MMAS-8
Health-related Quality of Life	Global Health	PROMIS
	Physical Function	PROMIS
	Pain Interference	PROMIS
	Fatigue	PROMIS
	Sleep	PROMIS
	Anxiety	PROMIS
	Social Function	PROMIS
Disease Severity	Disease Activity	SLAQ
	Organ Damage	SA-BILD
	Multimorbidity	CCHP
	Depression	PROMIS
Demographics	Age	Ad-hoc
	Education	Ad-hoc
	Employment	Ad-hoc
	Social Support	Ad-hoc
Health Service Utilization	ED visits	GA HDDB
	Hospitalizations	GA HDDB

MMAS: Morisky Medication Adherence Scale; PROMIS: Patient-Reported Outcome Measurement Information System; SLAQ: Systemic Lupus Activity Questionnaire; SA-BILD: Self-administered Brief Index Lupus Damage; ED: emergency department; GA HDDB: Georgia Hospital Discharge Database

representation of the AA female population in the CDSMP. The only exclusion criteria will be participation in the CDSMP in the past 5 years.

Women randomly selected will be mailed a flyer about the study and will receive a phone call by the Project Coordinator (PC) within the following week. During the phone call, the PC will assess the entry and exclusion criteria and will explain the study and level of participants' commitment needed to ensure study integrity. Interested participants will receive a packet with the consent, information of the CDSMP workshops schedule and location, a list of measures and study staff contact information. The PC will follow up with a phone call within 1 week to answer any questions and finalize the recruitment and CDSMP registration. Since this study entails minimal risk, interested GOAL participants will be consented via mail, e-mail, in person or telephone.

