## **Data Collection**

*Self-reported data.* Baseline assessment for WELL participants will take place within the 4 weeks that precede the start of the CDSMP classes. Post-intervention assessments will be scheduled at 6-, 12- and 18-month after baseline. All patient-reported measures will be collected online using the RedCap database. WELL participants will have a 2-week window to respond to the online surveys. Participants without computer access or those who do not complete the online survey within 2 weeks will be phone-interviewed.

All self-reported measures collected for WELL participants are included in the GOAL survey and summarized in Table 1. The time needed to complete the self-reported data survey will be between 20 and 40 minutes.

*Data on Health Service Utilization (HSU).* These data will be obtained by a well-established linkage procedure that links the GOAL cohort data with the GA Hospital Discharge Database (IRB#55041). This database contains claims data on emergency department (ED) visits and hospital admissions, including causes of admissions and ED visits.

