## **Analytic Methods**

Data will be organized and cleaned following quality control procedures after each wave, involving identifying outliers and inappropriate patterns of missing data. Psychometric properties of known measures will be compared with reported properties. For multi-item scales and indices, we will use methods such as reliability and factor analyses for data reduction and formation of composite summary variables. Confirmatory factor analyses will be conducted to evaluate the consistency and fit of individual items to a combined construct. We will make every attempt to avoid missing data by discouraging omissions, e.g., by ensuring confidentiality of responses in the

study description and encouraging participants to respond to each question.

For patient-reported and health services utilization outcomes, analysis of repeated measures data is needed that properly accounts for the correlation between multiple observations from the same participant. Two commonly used models to analyze such data will be employed: the mixed-effects model and the generalized estimating equations (GEE) approach. Both approaches allow for covariate adjustment. The results will be summarized with adjusted means and 95% confidence intervals for continuous outcomes. GEE can also be used to analyze count data (e.g., ED visits), ordinal data, and to perform a logistic regression of repeated binary responses within participants. Low classes attendance may attenuate outcome change and have a negative impact on study integrity. Longitudinal analyses will allow us to estimate the effect of CDSMP attendance (# of classes attended) on outcome change.

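### Chance decides only who is offered CDSMP, so enrolled versus usual care is an observational comparison; a supplementary by-draw analysis of linked utilization would use the randomness that exists

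*Combined protocol and SAP*

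**What the plan says.** On the draw, the first Recruitment and Informed Consent section says: "A random sample of SLE patients already recruited into the population-based GOAL study will be offered the opportunity to participate in the WELL Sub-study". It adds: "Each woman will have the same probability of being chosen at any stage of the sampling process", and gives the purpose as representation of the population. Drawn women are then phoned, screened against the criteria and told what commitment is needed. After that, "Interested participants will receive a packet with the consent".

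On the comparator, Design Overview and ClinicalTrials.gov Requirements both say: "AA women from the GOAL cohort non-selected to be assigned to the intervention will comprise the usual care group". Sources of Materials requires the comparator to meet the same entry criteria as the WELL group and states that the two groups' outcomes will be compared. Its wording for the comparator is looser, covering GOAL members under usual care without saying that they were not drawn.

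On analysis, Analytic Methods states that "analysis of repeated measures data is needed that properly accounts for the correlation between multiple observations from the same participant". It names mixed models and GEE, says "Both approaches allow for covariate adjustment", and promises adjusted means for continuous outcomes. It lists no covariates.

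On data, Data Collection says "All self-reported measures collected for WELL participants are included in the GOAL survey and summarized in Table 1". ED visits and hospitalizations come from linking the GOAL cohort to the state discharge database (Data Collection; Sources of Materials).

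**The concern.** The random step separates drawn from non-drawn women. It does not separate enrolled women from usual care. The enrolled group contains only accepters; usual care contains would-be accepters and would-be decliners together. If accepters would have followed a different course anyway, the comparison attributes part of that difference to the programme, and it could do so in either direction.

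Repeated measures and adjustment can remove stable, measured differences. They cannot show that differences in trend, or in unmeasured willingness, are gone. The stated aim is the programme's effect on patient-reported outcomes and utilization, so this bears on the main question.

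The draw would also support a comparison that acceptance cannot distort, and linked utilization does not require a woman to have enrolled. The protocol plans no such comparison and does not say that the draw list is kept for analysis. Without the list, that comparison could not be recovered later.

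**Working it through.** **The plan's own figure.** There is none to reproduce. Enrolment is 150, raised to 168 because of a waiting list and rescheduling. No effect size, event rate, power, acceptance rate or usual-care size is given.

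**Inputs.** From the documents: 168 enrolled. Assumed: acceptance p among drawn eligible women; eligible pool N of 400, 600 or 800; 1.5 ED visits per woman; negative-binomial dispersion k = 1; two-sided 5% level and 80% power (multiplier 2.80).

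**Step 1: possible bias.** Let r be the decliner-to-accepter ratio of the visit rate left after adjustment. With no programme effect, enrolled versus usual care shows a rate ratio of 1/(p + (1 − p)r).

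- p = 0.5, r = 1.2: 1/(0.5 + 0.5 × 1.2) = 1/1.1 = 0.91.
- p = 0.5, r = 1.1: 1/1.05 = 0.95. With r = 0.9: 1/0.95 = 1.05, the opposite direction.
- r = 1.2 with p = 0.3, 0.7, 0.9: 0.88, 0.94, 0.98.
- r = 1: no bias at any p.

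**Step 2: precision of a by-draw comparison.** Drawn = 168/p; undrawn = N − 168/p. SE of the log rate ratio = √[(1/1.5 + k)(1/n₁ + 1/undrawn)], with n₁ = 168/p by draw and n₁ = 168 for enrolled versus usual care. Detectable ratio = exp(−2.80 × SE). Implied ratio in participants = 1 − (1 − offer ratio)/p. This last step assumes equal untreated rates in accepters and decliners and no effect of the offer on decliners.

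Example, N = 800, p = 0.5: SE = √[1.667 × (1/336 + 1/464)] = 0.0925; exp(−0.259) = 0.77; 1 − 0.228/0.5 = 0.54.

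| N | p | Drawn | Undrawn | By-draw ratio | In participants | Enrolled v usual care |
|---|---|---|---|---|---|---|
| 800 | 0.9 | 187 | 613 | 0.74 | 0.71 | 0.73 |
| 800 | 0.7 | 240 | 560 | 0.76 | 0.65 | 0.73 |
| 800 | 0.5 | 336 | 464 | 0.77 | 0.54 | 0.72 |
| 800 | 0.3 | 560 | 240 | 0.76 | 0.19 | 0.70 |
| 600 | 0.5 | 336 | 264 | 0.74 | 0.49 | 0.70 |
| 400 | 0.5 | 336 | 64 | 0.61 | 0.22 | 0.59 |

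With N = 600 and p = 0.3 only 40 women stay undrawn and no participant effect is detectable. With N = 400 and p = 0.3 the pool is exhausted (168/0.3 = 560).

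These figures treat the draw as a single event with full follow-up. They leave out loss of control time when undrawn women are drawn later, and the lag from draw to class start (an assumed 3 months would be 3/18 = 17% of an 18-month window).

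**Step 3: total error for the effect in participants.** N = 800, r = 1.2, log scale. Enrolled versus usual care combines bias and SE: at p = 0.5, √(0.095² + 0.116²) = 0.15. By-draw, rescaled by 1/p (an approximation near no effect), gives 0.0925/0.5 = 0.185. At p = 0.3, 0.7 and 0.9 the pairs are 0.18 v 0.33, 0.13 v 0.14 and 0.114 v 0.120.

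**The case against.** The strongest reply is that the plan is sound for its purpose and that the remedy is weaker than the problem. The draw was made for representation. Both groups face the same criteria, adjustment is planned for continuous outcomes, and the Table 1 measures are collected on both sides. Those measures include medication adherence and communication with physicians, arguably the nearest proxies for engagement. For the effect in participants, Step 3 shows larger total error for by-draw than for the biased comparison in every r = 1.2 case at N = 800. By-draw also answers a different question, the effect of the offer.

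Much of this stands. It rules out putting by-draw in place of the adjusted comparison, and it makes the addition conditional on pool size and acceptance. It does not make the adjusted comparison randomised, and it gives no assurance about trend or unmeasured willingness. The mention of outcome change in Analytic Methods does not help either, because it concerns class attendance and not the comparison of groups.

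A reader might infer that the protocol passes off an observational comparison as randomised. It does not. ClinicalTrials.gov Requirements speaks of prospective assignment to evaluate the programme's effect, but no section calls the group comparison randomised. A reader might also infer that decliners are placed in usual care. Design Overview and ClinicalTrials.gov Requirements already restrict that group to non-selected women; only the looser wording in Sources of Materials leaves doubt.

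**Conclusion.** The point holds as a low-cost improvement. Random selection covers the offer only, the enrolled-versus-usual-care comparison is observational, and the plan contains no analysis that uses the draw. This reading of the text is firm.

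The size is not known. The documents give no acceptance rate, accepter-decliner difference, pool size or event rate. The 0.91 in Step 1 is an illustration; other assumed values give no bias, or bias the other way. It would be tempting to conclude that the trial will overstate benefit, or to quote an inflated false-positive rate. The documents support neither. If nearly all drawn women accept, the concern is small.

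Nor do the documents establish that an unbiased comparison is ready to run. That depends on a retained draw list, permission to use decliners' linked data, and enough undrawn women.

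**What to change.** 1. Keep the list and dates of drawn women. Report numbers drawn, reached, eligible and accepting; the recruitment reports under Data accuracy and protocol compliance are a natural place.
2. Add a supplementary by-draw analysis of linked ED visits and hospitalizations: all drawn women, including decliners and those not reached, against all non-drawn women, with only the criteria known from GOAL data applied alike to both. Count from the draw date, because "Baseline assessment for WELL participants will take place within the 4 weeks that precede the start of the CDSMP classes" and neither decliners nor non-drawn women have a class start. Compare within draw stage and censor non-drawn women at any later draw. Proceed once use of decliners' linked data is confirmed and if enough women remain undrawn.
3. Keep enrolled versus usual care as an adjusted comparison and label it observational. Name the covariates: the last pre-programme GOAL value of the outcome and of the chosen Table 1 measures, including medication adherence and communication with physicians. For usual care, use the survey nearest a matched index date. Never adjust for post-programme values, since several Table 1 measures are themselves outcomes.
4. Align the comparator wording in Sources of Materials with Design Overview, so that drawn decliners are not counted as usual care.

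**Cost.** Analysis text, an index-date rule, a retained list and one permission check; no new participants or visits. Sources of Materials describes linkage approval for the GOAL cohort but names only the CDSMP and usual care groups, hence the check. By-draw estimates the effect of the offer, is diluted by refusal, and may be uninformative at acceptance of about 0.5 or lower or with a small pool. Prior CDSMP use is assessed by phone, so it may be unknown for women not called.

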### **SOURCES OF MATERIALS**

Involvement of human subjects for this study includes the completion of surveys, participation in the Chronic Disease Self-Management Program (CDSMP) and optional semi-structured interviews among those participants enrolled into the WELL cohort. Surveys will be done at four intervals (baseline, 6-month, 12-month, and 18-month post baseline) by computer or by telephone. WELL participants will attend the CDSMP workshop at a convenient location. Through quota-sampling, a purposive sample of 25 CDSMP participants will be enrolled in a qualitative substudy to participate in semi-structured interviews. Interviews will be conducted in-person at two intervals (pre- and post- CDSMP workshop completion).

As previously discussed, the types of data that will be obtained from WELL (CDSMP) participants are self-reported data from questionnaires and semi-structured interviews. Validated instruments will be used to examine self-management behaviors and health-related quality of life. NIH-PROMIS measures will be used to assess the specific health-related quality of life domains. Self-administered data will be collected

through online surveys using the Research Electronic Data Capture (REDCap), which is a mature, HIPPA compliant secure web application for building and managing online surveys and databases. Participants may also request to have the questionnaire interviewer-administered via telephone.

Qualitative semi-structured interviews will be designed to explore personal definitions of successful self-management, health-related quality of life, health service utilization and challenges to the successful management of SLE. Interviews will be audio recorded and transcribed verbatim. Audio recordings and transcripts will be stored on an encrypted password-protected computer. Any printed transcripts will be stored in locked cabinets.

De-identified data routinely collected from those GOAL participants receiving usual care, who meet the same inclusion and exclusion criteria than WELL participants (CDSMP group), will be used to enable the comparison of study outcomes between the CDSMP group and the usual care group.

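### The usual-care group is defined with and without the WELL eligibility criteria, and the plan describes no way to apply the 5-year CDSMP exclusion to women who were not drawn

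*Combined protocol and SAP*

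**What the plan says.** Three sections describe the comparator. The Design Overview says that "AA women from the GOAL cohort non-selected to be assigned to the intervention will comprise the usual care group", and ClinicalTrials.gov Requirements uses the same sentence. Neither adds a condition. Sources of Materials says that de-identified data from usual-care GOAL participants "who meet the same inclusion and exclusion criteria than WELL participants (CDSMP group), will be used to enable the comparison of study outcomes" between the two groups.

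The criteria are in the first Recruitment and Informed Consent section, the one containing Table 1. A WELL participant must be "resident of one of the metropolitan Atlanta counties where community-based CDSMP classes are provided", and "The only exclusion criteria will be participation in the CDSMP in the past 5 years". The same section describes the draw: "A random sample of SLE patients already recruited into the population-based GOAL study will be offered the opportunity" to join. Drawn women are mailed a flyer and then telephoned. "During the phone call, the PC will assess the entry and exclusion criteria".

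Usual-care women are not contacted for WELL. They contribute their routine annual GOAL assessments and the hospital discharge linkage. Analytic Methods does not define the comparator population. It says the models allow covariate adjustment but names no covariates.

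**The concern.** The random draw is the main protection in this design. Before any filtering, drawn and undrawn women differ only by chance. If one side is then filtered on facts that are not collected on the other, that balance is lost and the contrast reflects eligibility as well as the program.

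Both criteria could matter. Prior CDSMP participation is exposure to the intervention itself, and the Background calls the program widely disseminated, so prior exposure cannot be assumed absent. Women with such exposure would be removed from WELL but could remain in usual care. County of residence plausibly bears on emergency visits and admissions, which are study outcomes. Covariate adjustment cannot deal with a variable that was never recorded.

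Because Analytic Methods is silent on the comparator, an analyst could also defend either definition after seeing the data.

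**Working it through.** **1. Definitions side by side.**
- Design Overview and ClinicalTrials.gov Requirements: all African American GOAL women not selected.
- Sources of Materials: the usual-care women who meet the WELL criteria.
- Analytic Methods: no definition.

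The second group is a subset of the first. The two coincide only if every undrawn woman is eligible.

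**2. Source of each criterion, by group.**
- *County, drawn women:* assessed in the coordinator's call.
- *County, undrawn women:* no step described. Flyers are mailed before any call, which implies that GOAL holds addresses, so a county filter is probably feasible. It is not stated as planned.
- *CDSMP in the past 5 years, drawn women:* assessed in the same call.
- *CDSMP in the past 5 years, undrawn women:* no step and no source described. Data Collection says the WELL self-report measures are in the GOAL survey and summarized in Table 1. Table 1 lists neither county nor CDSMP history.

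The gap that remains is therefore mainly the 5-year exclusion.

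**3. Size, as illustration only.** The plan gives no alpha, power, SD, effect size or comparator size, so there is no stated figure to reproduce. The only number taken from it is WELL enrollment, nT = 168. Everything else is assumed:
- f, the ineligible share of usual care: 5% to 30%
- d, the outcome difference between ineligible and eligible usual-care women: 0.2 to 0.5 SD
- nC, the usual-care group size: 150 to 500
- two-sided alpha of 0.05

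Shift in the usual-care mean: b = f × d.
- Low: 0.05 × 0.2 = 0.01 SD
- Middle: 0.30 × 0.2 = 0.06 SD
- High: 0.30 × 0.5 = 0.15 SD

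Standard error of a two-group difference: SE = sqrt(1/nT + 1/nC).
- nC = 150: sqrt(1/168 + 1/150) = 0.112 SD
- nC = 500: sqrt(1/168 + 1/500) = 0.089 SD

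Type I error under a shift b: Φ(−1.96 − b/SE) + Φ(−1.96 + b/SE).

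| b (SD) | nC = 150 | nC = 500 |
|---|---|---|
| 0.01 | 5.1% | 5.1% |
| 0.06 | 8.3% | 10.3% |
| 0.15 | 26.7% | 39.1% |

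If the comparator is limited to verified-eligible women, f = 0 and this source of bias is zero. The calculation compares outcome levels at one time point and ignores repeated measures and adjustment.

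**The case against.** The strongest reply is that Sources of Materials refines the overview and does not conflict with it. It is the section that says which usual-care data enter the comparison, and nothing says that ineligible women will be analyzed. That largely stands. A reader might infer from the broad sentence that the comparator will contain women who could never have entered WELL. The documents do not support this, because the restriction is stated once and the issue is at most ineligibility at the time of the draw.

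A reader might also infer that the restricted definition cannot be applied at all. That goes too far. Residence can probably be taken from cohort addresses. The parent cohort's documents are not available here, and Table 1 summarizes this study's measures, so it does not prove that GOAL lacks CDSMP history. The equal-probability sentence in Recruitment and Informed Consent even leaves room for a sampling frame already limited to the class counties. What survives is that no method is written down, and that for prior CDSMP use no data source is even implied.

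Finally, a stable difference in outcome level would largely cancel in an analysis of change from baseline. Only a difference in change would then bias the result. This is fair, and it is one reason why the figures above are illustrative.

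**Conclusion.** The point holds in a limited form. The comparator has two wordings. The restricted one is evidently intended, but the plan gives no means of applying the 5-year exclusion to undrawn women, so that exclusion would in practice fall on one group only.

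Size and direction cannot be determined from the documents. Prior CDSMP users left in usual care could pull a true effect toward zero. The direction for women outside the class counties is unknown. If few women are ineligible, the effect is negligible.

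It would be tempting to express the bias as a share of a detectable difference. Assuming shares of 20% to 40% and differences of 0.1 to 0.3 SD gives 0.02 to 0.12 SD. With 168 women assumed in each group, the difference detectable with 80% power is (1.96 + 0.842) × sqrt(2/168) = 0.306 SD, so the ratio runs from 0.02/0.306 = 7% to 0.12/0.306 = 39%. The upper value is the worst corner of a grid in which the share, the difference and the control count are all assumed. Nothing in the plan supports a share that large for prior CDSMP use, and the 39% should not be quoted as the size of the problem.

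The change is still worth making. It removes an avoidable asymmetry at little cost and settles the comparator before analysis.

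**What to change.** 1. Carry the eligibility clause from Sources of Materials into the Design Overview and ClinicalTrials.gov Requirements, and state the same population in Analytic Methods.
2. Apply the county criterion to both groups from the same GOAL residence records: in the sampling frame for any further draw, and at analysis for draws already made. The April 2019 enrollment increase was made for women on a waiting list, so some draws have probably taken place. Because usual-care data reach the study de-identified, the filter should be run before identifiers are removed.
3. Add one question on CDSMP participation, with dates, to the routine GOAL survey, and apply the 5-year criterion to both groups from that item. Dates are needed so that earlier periods can be classified retrospectively.
4. Where the item is missing for usual-care women, do not assume no exposure. Report a sensitivity analysis, for example with those women included and then excluded.

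The cost is wording in three sections, a filter on residence records that GOAL probably already holds, one added item in a parent-cohort survey, and a somewhat smaller usual-care pool.
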